R _{ac} (C _{max})	Accumulation ratio calculated using C _{max}
R ² adjusted	Adjusted correlation coefficient
SAP	Statistical Analysis Plan
SD	Standard deviation
t _½	Apparent terminal phase half-life
t _{last}	Time of last quantifiable concentration

Abbreviation / Acronym**Definition / Expansion**

TLFs	Tables, listings and figures
T _{max}	Time of occurrence of C _{max}
WNL	WinNonlin
λ _z	Terminal elimination rate constant

STATISTICAL ANALYSIS PLAN

This Statistical Analysis Plan (SAP) details the methodology to be used in analyzing the pharmacokinetic (PK) data and outlines the PK Tables, Listings and Figures (TLFs). It describes the variables and populations, anticipated data transformations and manipulations and other details of the analyses not provided in the Clinical Study Protocol (CSP).

The PK analyses described are based on the final CSP Version 4.0, dated 13 December 2016. The SAP will be finalized prior to database lock and describes the pharmacokinetic analysis as it is foreseen when the study is being planned. If circumstances should arise during the study rendering this analysis inappropriate, or if improved methods of analysis should arise, updates to the analyses may be made. Any deviations from the SAP after database lock, reasons for such deviations and all alternative or additional statistical analyses that may be performed, will be described in a SAP Addendum.

1. PRIMARY OBJECTIVE

To evaluate the PK and safety profile of multiple ascending dose levels of NT-814 compared to placebo, by once daily administration of each dose for 14 days

2. PRIMARY PHARMACOKINETIC ENDPOINTS

The PK endpoints are:

- peak concentration (C_{\max})
- time of occurrence of C_{\max} (T_{\max})
- area under the curve (AUC) from time zero to the time of the last quantifiable concentration (AUC_{0-t})
- AUC in the dosing interval ($AUC_{0-\tau}$, synonymous with AUC_{0-24})
- AUC from time zero extrapolated to infinity ($AUC_{0-\infty}$)
- apparent terminal phase half-life ($t_{1/2}$)
- apparent clearance (CL/F)

The PK parameters will be derived on Day 1, Day 7, and Day 14, as appropriate.

3. STUDY DESIGN

This is a multi-center, double-blind, randomized, placebo-controlled multiple ascending dose trial in post-menopausal women with vasomotor symptoms. Subjects will be recruited into sequentially dosed cohorts; Cohort 1 (50 mg NT-814 or placebo), Cohort 2 (100 mg NT-814 or placebo), Cohort 3 (150 mg NT-814 or placebo) and Cohort 4 (300 mg NT-814 or placebo). For each cohort, subjects will enter a 4-week screening period to determine eligibility. Twenty eligible subjects will be randomized per cohort (15 active and 5 placebo).

On Day 1, the subjects will be randomized in a 3:1 ratio to once daily (morning) doses of NT-814 or placebo, to be taken for a total of 14 days. Subjects will be monitored as an inpatient from Day -1 to Day 8 and will undergo blood draws for intensive PK sampling, safety monitoring and for impact on blood hormonal profiling as well as 24-hour skin conductance measurements and continuous completion of hot flash diaries.

Subjects will be discharged from the clinic on Day 8 without any monitoring devices, providing there are no safety concerns and will undergo dosing for a further 5 days as an outpatient. Subjects will be instructed to continue recording details of the hot flashes experienced, using the twice daily diary. They will be provided with the continuous daily diary and instructed to start completing this upon waking on the morning of Day 14 prior to admission to the clinic. They will be re-admitted to clinic on the morning of Day 14 for the final dose and undergo the same assessments with the same devices including Holter and skin conductance as Day 1. Subjects will be discharged following the 24-hour post Day 14 assessments (Day 15). Subjects will return to the clinic, as outpatients, for a single PK sample on the mornings of Days 16 and 17 (48 hours and 72 hours after the Day 14 dose respectively).

Throughout the study, subjects will be closely monitored for safety including assessments of AEs, 12-lead ECGs, arterial oxygen saturation using pulse oximetry, vital signs (sitting and standing BP, heart rate, oral body temperature, and respiration rate), clinical labs and physical examinations.

Blood samples for PK analysis will be collected at the following time points on Day 1, Day 7 and Day 14: Pre-dose, 0.5, 1.0, 1.5, 2.0, 2.5, 3.0, 4.0, 5.0, 6.0, 8.0, 12.0, 24.0 hours. Additional sampling times of 48 and 72 hours will be collected following the Day 14 dose. The pre-dose sample will be collected within 30 minutes prior to dose administration.

4. STUDY POPULATION

Post-menopausal female subjects 40-65 years of age

5. STATISTICAL BASIS FOR SAMPLE SIZE

The planned sample size is 20 subjects per cohort, with 15 active and 5 placebo. This is deemed enough to provide sufficient separation of exposures between dose groups and to allow for an assessment of safety versus dose group/exposure. Assuming a standard deviation on the log scale of 0.413 for plasma AUC_{0-24} (based on Day 7 mean AUC_{0-24} data for 200 mg from study MNK111857), 15 active subjects per cohort provides close to 80% power at a type I error rate of 0.1 to detect a difference from one in the ratio of geometric means between the two highest possible dose levels (and greater than 90% power for the middle two dose levels) given the previously seen slightly greater than dose proportionality increase in systemic exposure. The placebo subjects are included primarily to provide a reference group for comparison of safety in the target population.

6. RANDOMIZATION

On Day 1, the subjects will be randomized in a 3:1 ratio to once daily (morning) doses of NT-814 or placebo, to be taken for a total of 14 days.

7. ANALYSIS POPULATIONS

The following data sets will be used for the analysis:

- **Safety Analysis Set:** All subjects who receive at least one dose of double-blind study drug. Subjects will be analyzed according to treatment received.
- **Pharmacokinetic Analysis Set (PKAS):** All subjects who received at least one dose of active study drug and for whom the PK data are considered sufficient. Subjects or data may be excluded from the PKAS at the discretion of the PK Scientist, including, but not limited to the following:
 - Concomitant medication which could render the plasma concentration-time profile unreliable

Any data excluded will be discussed in the CSR. Any excluded subject will have their concentration and PK parameter data listed only. Subjects who receive placebo will not be part of the PKAS.

Analysis Sets will be identified prior to the unblinding of the study data.

8. STATISTICAL ANALYSIS CONVENTIONS

8.1 Pharmacokinetic Variables

Derivation of PK parameters will be the responsibility of Quantitative Clinical Development (QCD), PAREXEL International. The PK parameters will be determined for NT-814 in plasma following single and multiple dose administration.

8.1.1 Handling of Values Below the Limit of Quantification

All plasma concentrations below the lower limit of quantification (LLOQ) or missing data will be labeled as below the limit of quantification (BLQ) or missing, respectively, in the concentration data listings.

Considerations in the handling of BLQ data for the generation of plasma PK Parameters

BLQ values will be imputed in the PK concentration dataset used for the derivation of PK parameters. The following rules will be applied:

- BLQs at the beginning of a subject profile (i.e. before the first incidence of a measurable concentration) will be assigned to zero.
- BLQs at the end of a subject profile (i.e. after the last incidence of a measurable concentration) will be set to missing.
- Single BLQs which fall between two measurable concentrations will be set to missing.
- Consecutive BLQs which fall between measurable concentrations will be set to missing. Measurable concentrations after consecutive BLQs will also be set to missing.

Considerations in the handling of BLQ data for plotting of individual plasma PK concentration data

BLQ values will be imputed for individual concentration-time plots according to the following rules:

- BLQs at the beginning of a subject profile (i.e. before the first incidence of a measurable concentration) will be assigned to zero.
- BLQs at the end of a subject profile (i.e. after the last incidence of a measurable concentration) will be set to missing.
- Single BLQs which fall between two measurable concentrations will be set to missing.

- Consecutive BLQs which fall between measurable concentrations will be set to zero. Measurable concentrations after consecutive BLQs will be retained.

For linear plots, zero concentration value(s) will be included in the plot.

For log-linear plots, zero concentration value(s) will be assigned a missing value.

A reference line indicating LLOQ may be included on plots.

Considerations in the handling of BLQ data for summarizing plasma PK concentration data

BLQ values will be imputed for mean/median concentration-time plots and tabular summaries according to the following rules:

- All BLQ values will be set to zero, except when an individual BLQ falls between two measurable values, in which case it will be set to missing.
- All BLQ values will be substituted with the LLOQ for calculation of geometric means and geometric CVs
- Measurable concentrations after consecutive BLQs will be set to missing.

Zero mean or median values will be included in tabular summaries.

A high proportion of BLQ values may affect derivation of standard deviation; if more than 30% of values at a time-point are imputed, then standard deviation (SD) will not be displayed.

Tabular summaries for concentration-time data will report N (number of subjects who received treatment) and n (number of subjects with non-missing values).

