8.2.3 Pharmacokinetic Concentrations and Variables

Pharmacokinetic plasma concentration data will be listed by cohort and subject including actual sampling times relative to dosing. Plasma concentrations will be summarized by cohort, day and nominal time point. The following descriptive statistics will be presented for plasma concentrations obtained at each nominal time point: n, arithmetic mean, SD, coefficient of variation (CV%), geometric mean (GM), geometric coefficient of variation (GCV%), median, minimum and maximum values.

Plasma pharmacokinetic parameters will be listed by cohort, subject and day, and summarized by cohort and day. Descriptive statistics for calculated PK parameters will include: n, arithmetic mean, SD, CV%, GM, GCV%, median, minimum and maximum values. For T_{max} , only median, minimum and maximum values will be presented. No descriptive statistics will be determined when fewer than three individual PK parameters are available.

Individual plasma concentration versus actual times will be plotted by cohort and day in linear and semi-logarithmic scale. Combined individual plasma concentrations versus actual times will be plotted by cohort and day.

Arithmetic mean plasma concentrations versus nominal times will be presented by day on a linear scale and semi-logarithmic scale. All treatments will be overlaid on the same plot.

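### As written, the PK SAP rule for concentration summaries drops all 11 later measurable values of any subject who is BLQ at both Day 1 predose and 0.5 h; a minor wording error limited to descriptive Day 1 means

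*SAP*

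**What the plan says.** PK SAP section 8.1.1 gives three sets of rules for BLQ values.

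- **PK parameter derivation.** Leading BLQs have their own rule: "BLQs at the beginning of a subject profile (i.e. before the first incidence of a measurable concentration) will be assigned to zero". The deletion step comes straight after a positional limit: "Consecutive BLQs which fall between measurable concentrations will be set to missing. Measurable concentrations after consecutive BLQs will also be set to missing".
- **Individual plots.** Leading BLQs again become zero, and for later values the rule is "Measurable concentrations after consecutive BLQs will be retained".
- **Mean/median curves and tables.** The scope is stated as "BLQ values will be imputed for mean/median concentration-time plots and tabular summaries according to the following rules". The first rule is "All BLQ values will be set to zero, except when an individual BLQ falls between two measurable values", in which case that value becomes missing. Geometric statistics use the LLOQ in place of a BLQ. The last rule is "Measurable concentrations after consecutive BLQs will be set to missing". There is no rule for leading BLQs, and the last bullet does not say where the consecutive BLQs must lie.

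Section 8.2.3 shows where the rule bites: "Plasma concentrations will be summarized by cohort, day and nominal time point". Nothing in the rest of section 8.1.1, or in sections 8.1.2 to 8.2.4, restores the missing limit.

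**The concern.** The Day 1 predose sample is taken before any drug, so it should be BLQ in every active subject. The next sample is at 0.5 h. If that one is BLQ too, the subject has two consecutive BLQs at the start of her profile. The literal summary rule then removes everything measurable that follows.

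The loss is not random, because it picks out subjects who absorb slowly. Her zero counts in the 0.5 h arithmetic mean but she is absent from the 1 h mean, so the set of subjects changes between adjacent points and the rise looks steeper than it was. Day 7 and Day 14 predose values should normally be measurable, so those days are largely spared and an overlay by day would compare differently selected subjects. In Table 1.1, which shows individual and summary concentrations together, the summary rows would not follow from the individual values. The Day 1 mean profile in Figure 1.2 would not match the parameters in Table 1.2, which keep these subjects.

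**Working it through.** The plan states no figure on this point, so there is none to reproduce. The check applies the written rule to the planned schedule and then sizes the effect under stated assumptions.

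**Inputs from the documents**
- Day 1 schedule (PK SAP section 3): predose, 0.5, 1, 1.5, 2, 2.5, 3, 4, 5, 6, 8, 12 and 24 h, which is 13 samples.
- Active subjects per cohort (PK SAP section 3): 15.
- LLOQ and probability of a BLQ at 0.5 h: not given.

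**Step 1: apply the rule to one Day 1 profile**

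| Case | Measurable values | Kept, literal rule | Kept, if limited to BLQs between measurable values |
|---|---|---|---|
| Predose and 0.5 h BLQ | 11 | 0 | 11 |
| Predose only BLQ | 12 | 12 | 12 |

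In the first case the literal rule gives 0, 0 and then missing at all 13 − 2 = 11 times from 1 to 24 h. The BLQ at 0.5 h is the trigger. With k such subjects, n from 1 h onward is 15 − k, that is 14, 12 or 10 for k = 1, 3 or 5.

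**Step 2: how often (assumed p)**

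Let p be the probability that a subject is BLQ at 0.5 h on Day 1. The chance of at least one affected subject in a cohort is 1 − (1 − p)^15, and the expected number is 15p.

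| p | Chance of at least one | Expected number |
|---|---|---|
| 0.02 | 0.26 | 0.3 |
| 0.05 | 0.54 | 0.75 |
| 0.10 | 0.79 | 1.5 |
| 0.20 | 0.97 | 3.0 |

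These values of p are a range for illustration. If p is 0, nothing happens.

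**Step 3: effect on the mean curve (assumed profile)**

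Assume C(t) proportional to exp(−0.1t) − exp(−t), that is ke = 0.1/h and ka = 1/h, with affected subjects following C(t − 0.75). The literal rule averages only the 15 − k unaffected subjects, so

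ratio of literal mean to full mean = 15·C(t) / [(15 − k)·C(t) + k·C(t − 0.75)].

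Example at 1 h, k = 3: C(1) = 0.537 and C(0.25) = 0.1965, so 15 × 0.537 / (12 × 0.537 + 3 × 0.1965) = 8.055 / 7.034 = 1.145.

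| Time | k = 2 | k = 3 | k = 5 |
|---|---|---|---|
| 1 h | 1.092 | 1.145 | 1.268 |
| 1.5 h | 1.040 | 1.061 | 1.105 |
| 2 h | 1.017 | 1.026 | 1.045 |
| 2.5 h | 1.006 | 1.009 | 1.015 |
| 3 h | 1.000 | 0.999 | 0.999 |
| 24 h | 0.990 | 0.985 | 0.975 |

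The 0.5 h arithmetic mean is not changed, because the zeros stay in.

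**The case against.** **The intent was probably narrower.** In the parameter block, too, the deletion sentence carries no limit of its own; it takes it from the sentence before. The first summary bullet deals with a single BLQ inside a profile, so the last bullet can be read as its counterpart for runs inside a profile. That is a fair account of intent, and a reader should not infer that the plan means to delete slow absorbers. But the first summary bullet states the positional limit when it wants it and the last does not, so someone programming or checking the text as written would delete valid data.

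**The event may never occur.** A reader might infer that lags are expected because protocol section 11.3.3 mentions t_lag. That is its only mention among the PK plans: it is not a PK endpoint in the protocol or either analysis plan, and the PK SAP gives no method for it. Protocol section 9.2 gives a rat C_max of 6500 ng/mL and a margin of about 14-fold at 50 mg, which implies an anticipated C_max near 6500 / 14 ≈ 460 ng/mL at the lowest dose, possibly lower on Day 1. Without the LLOQ, this cannot show whether any subject would be BLQ at 0.5 h. This objection stands in full.

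**No primary PK result or decision depends on it.** It is tempting to say that the primary PK evaluation is compromised, but the documents do not support that. The PK endpoints are parameters, derived under the block that carries the limit. Dose proportionality uses Day 7 AUC and C_max. The escalation limit is a geometric mean AUC. The concentration–QTc model pairs individual concentrations with QTcF. Individual plots keep the values, and the summary rule does not govern the listings. This also stands.

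**The loss would be visible, and 27% is the extreme.** Concentration tables report both N and n, so a fall in n from 1 h onward would show, although showing it does not correct it. The 27% needs one third of a cohort affected and is the worst time point shown in the illustration.

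**Conclusion.** The rule is wrong as written, and the matter is minor. That such a subject loses 11 of 11 measurable Day 1 values follows from the text and the sampling schedule, with no assumption beyond BLQ results at predose and 0.5 h.

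The size of the bias rests on the assumed one-compartment profile, the 0.75 h lag and 2 to 5 affected subjects of 15. On those assumptions it is material only at about 1 to 2 h of a descriptive curve and is small from 2.5 h onward. The true frequency cannot be found from the documents and may be zero.

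**What to change.** Replace the last bullet of the summary rules in PK SAP section 8.1.1 with one that says two things. Measurable concentrations are set to missing after consecutive BLQs only when those BLQs lie between measurable concentrations in the same profile. Measurable concentrations that follow BLQs at the start of a profile are kept.

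This aligns the summary block with the parameter-derivation block. It costs one sentence and needs no new data, and I see no statistical drawback. If the database is already locked, the PK SAP's own introduction calls for the change to be recorded in a SAP Addendum.

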8.1.2 Pharmacokinetic Parameter Calculation Methods

PK parameters will be calculated by non-compartmental analysis methods from the concentration-time data using Phoenix® WinNonlin® (WNL) Professional (Version 6.3 or higher) following these guidelines:

- Actual sampling times relative to dosing rather than nominal times will be used in the calculation of all derived PK parameters.
- There will be no imputation of missing data.
- Any subjects with missing concentration data will be included in the PK analysis set provided that at least C_{max} and AUC_{0-t} can be reliably calculated.

PK parameters will be estimated according to the following guidelines:

- C_{\max} will be obtained directly from the concentration-time data.
- T_{\max} is the time at which C_{\max} is observed.
- λ_z will be estimated at terminal phase by linear regression after log-transformation of the concentrations:
 - Only those data points that are judged to describe the terminal log-linear decline will be used in the regression.
 - A minimum number of three data points in the terminal phase will be used in calculating λ_z with the line of regression starting at any post- C_{\max} data point (C_{\max} should not be part of the regression slope). The adjusted correlation coefficient (R^2 adjusted) in general should be greater than 0.90. Any value < 0.90 but ≥ 0.80 will be flagged but may be used at the PK Scientist's best knowledge and judgment; any value < 0.80 will be excluded from the analysis.
 - The interval used to determine λ_z should be equal or greater than 1.5-fold the estimated half-life or otherwise flagged and excluded from the analysis.
- $t_{1/2}$ will be calculated as $\ln 2 / \lambda_z$.
- AUC is calculated by the linear up/log down method (linear method will be employed for all incremental trapezoids arising from increasing concentrations and the logarithmic method will be used for those arising from decreasing concentrations).

$$AUC_{0-t} = \int_0^t C(t) dt$$

$$AUC_{0-inf} = \int_0^t C(t) dt + \int_t^{\infty} C(t) dt = AUC_{0-t} + C_t / \lambda_z$$

$AUC_{0-\tau,ss}$ will be calculated at steady state during the time interval between consecutive doses

- C_t is last observed quantifiable concentration.
- %AUC_{ex} will be calculated as $(1 - [AUC_{0-t} / AUC_{0-inf}]) \times 100$. The %AUC_{ex} should not exceed 20% for each individual profile. If the %AUC_{ex} is more than 20%, the individual result should be flagged and mentioned in the report as well as all parameters depending on AUC_{0-inf} . If the %AUC_{ex} is greater than 30% the value and all dependent parameters should be flagged and excluded from the analysis.
- CL/F will be calculated as dose/ AUC_{0-inf} , parent drug only.

The following PK parameters may also be derived.

- $R_{ac}(AUC)$ Accumulation ratio is calculated as: $AUC_{0-\tau}$ (last dose interval)/ $AUC_{0-\tau}$ (first dose interval).
- $R_{ac}(C_{max})$ Accumulation ratio is calculated as: C_{max} (last dose interval)/ C_{max} (first dose interval).

8.2 Statistical Analysis Methods

8.2.1 Software

Statistical analysis of PK parameters will be performed using Phoenix® WinNonlin® (WNL) Professional (Version 6.3 or higher) and will be based on the PK analysis set (PKAS).

8.2.2 Missing Data

There will be no imputation of missing data. The details on handling PK data below the lower level of quantification (LLOQ) are given in Section 8.1.2.

8.2.3 Pharmacokinetic Concentrations and Variables

Pharmacokinetic plasma concentration data will be listed by cohort and subject including actual sampling times relative to dosing. Plasma concentrations will be summarized by cohort, day and nominal time point. The following descriptive statistics will be presented for plasma concentrations obtained at each nominal time point: n, arithmetic mean, SD, coefficient of variation (CV%), geometric mean (GM), geometric coefficient of variation (GCV%), median, minimum and maximum values.

Plasma pharmacokinetic parameters will be listed by cohort, subject and day, and summarized by cohort and day. Descriptive statistics for calculated PK parameters will include: n, arithmetic mean, SD, CV%, GM, GCV%, median, minimum and maximum values. For T_{max} , only median, minimum and maximum values will be presented. No descriptive statistics will be determined when fewer than three individual PK parameters are available.

Individual plasma concentration versus actual times will be plotted by cohort and day in linear and semi-logarithmic scale. Combined individual plasma concentrations versus actual times will be plotted by cohort and day.

Arithmetic mean plasma concentrations versus nominal times will be presented by day on a linear scale and semi-logarithmic scale. All treatments will be overlaid on the same plot.

